11.2 Statistical Methods

11.2.1 Statistical Analysis Sets

Full Analysis Set

The full analysis set (FAS) will consist of all patients who received at least 1 dose of study drug in Study A4250-008. The FAS will be the primary analysis set for all analyses unless otherwise specified.

11.2.2 Methods of Statistical Analyses

11.2.2.1 General Principles

Descriptive statistics will mainly be used in this open-label extension study. Patients with BRIC will be presented separately in efficacy assessments. All statistical analyses will be performed using SAS version 9.3 or higher.

The primary analysis will be performed after the last patient (from Cohort 1 or 2) completes the 72-week treatment period. Analyses during the extension period will consist of safety

summaries and other evaluations on an ongoing basis per the schedule of assessment for the extension period.

Baseline 1 will be defined as the last value prior to treatment start in Study A4250-005 for Cohort 1 patients.

Baseline 2 will be defined as the last value prior to treatment start in Study A4250-008 for all patients. Baseline 2 will be used in all analyses unless otherwise specified.

Descriptive statistics will be summarized for Cohort 1, Cohort 2 excluding BRIC, Cohort 2 BRIC, and combined Cohort 1 + Cohort 2 excluding BRIC. Within Cohort 1, the following subgroups will be presented: ‘A4250 40 µg/kg/day (005) to 120 µg/kg/day (008)’, ‘A4250 120 µg/kg/day (005) to 120 µg/kg/day (008)’, ‘A4250 40 µg/kg/day (005) and 120 µg/kg/day (005) to 120 µg/kg/day (008)’, and ‘placebo (005) to 120 µg/kg/day (008)’. Within Cohort 2 excluding BRIC, 3 subgroups (‘40 µg/kg/day’, ‘40 µg/kg/day to 120 µg/kg/day’, and ‘120 µg/kg/day’) will be presented. Cohort 1 Placebo to A4250 120 µg/kg/day will also be combined with Cohort 2 excluding BRIC for presentations.

11.2.2.2 Missing Data

Missing data will be reported descriptively. In general, imputations of missing observations will not be made. Any additional sensitivity analysis concerning missingness and details regarding handling of missing data will be described in the statistical analysis plan (SAP).

Continued collection of efficacy data for patients who discontinue treatment will be made as far as possible.

11.2.2.3 Demographic and Baseline Characteristics

For Cohort 1, descriptive summaries of demographics and other baseline characteristics (including medical and surgical history) will be presented overall using the FAS. For Cohort 2, descriptive summaries of demographics and other baseline characteristics will be presented overall for the full analysis set as well as by the underlying diagnostics subgroups.

Prior medication will be summarized overall using the full analysis set.

11.2.2.4 Subject Disposition

The following will be summarized overall by Cohort:

- Patients enrolled (who signed the informed consent)
- Patients treated
- Patients completing treatment
- Patients discontinuing treatment and reason
- Patients completing the study
- Patients withdrawing early (including withdrawal reason)

Additionally, patients enrolled, included in the FAS will be summarized by region by Cohort.

11.2.2.5 Evaluation of Primary Efficacy Variables

The proportion of positive pruritus assessments at the patient level over the 72-week treatment period will be summarized. A positive pruritus assessment is defined as a scratching score of ≤ 1 or at least a one-point drop from baseline on the Albireo ObsRO instrument. At each assessment, the AM score will be compared to the baseline AM average, and the PM score will be compared to the baseline PM average. Both AM and PM pruritus assessments will be included in the analysis of this endpoint. Baseline will be defined as the average score from 14 days prior to treatment start in Study A4250-008 for AM and PM, respectively.

Fasting serum bile acids baseline will be calculated as the average of the pre-dose value in Study A4250-008 (Visit 1) and the previous visit (Visit 8 in study A4250-005) for Cohort 1. Fasting serum bile acids baseline will be calculated as the average of Visit S-2 and the pre-dose Visit 1 values in Study A4250-008 for Cohort 2. The end value is the average of the values at Weeks 70 and 72 in study A4250-008.

The change from baseline over the Treatment Period in serum bile acids will be analyzed mainly by using descriptive statistics. Change over time will also be displayed using graphical presentations (e.g., a spaghetti plot which illustrates the change in both Study A4250-005 and Study A4250-008 by treatment group in Study A4250-005). In addition, change from baseline 1 to end of treatment will be analyzed by using one-sample T-test or Wilcoxon signed-rank test as appropriate.

As an exploratory analysis of pruritus and serum bile acids, a comparison of treatment with A4250 120 $\mu\text{g}/\text{kg}/\text{day}$ during the first 24 weeks of Study 008 vs placebo patients over the 24-week treatment period from Study 005 will be carried out.

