Patients in Cohort 2 will go through a screening period consisting of:

- Visit S-1: Screening Visit 1 (Days -56 to -35).

³ As of Protocol Amendment 6, patients entering Cohort 2 will start treatment at 40 µg/kg/day with the possibility to dose escalate to 120 µg/kg/day after 12 weeks if there is no improvement in pruritus based on investigator judgment.

- Visit S-2: Screening Visit 2 (Days -28 to -7)

Patients not meeting eligibility criteria may be re-screened after consultation with the Medical Monitor. Patients not fulfilling inclusion/exclusion criteria after 3 attempts are not allowed to rescreen.

Patients will have a minimum of 12 visits at the study site and 6 scheduled telephone contacts (see [Figure 1](#) and [Figure 2](#)) as follows:

- Visit 1: Screening/Inclusion Visit (Day 1; coincides with Visit 9 in Study A4250-005 for patients in Cohort 1)
- Visit 2: Week 4
 - Telephone contact 1: Week 8
- Visit 3: Week 12
 - Telephone contact 2: Week 18
- Visit 4: Week 22
- Visit 5: Week 24
 - Telephone contact 3: Week 30
- Visit 6: Week 36
 - Telephone contact 4: Week 42
- Visit 7: Week 46
- Visit 8: Week 48
 - Telephone contact 5: Week 54
- Visit 9: Week 60
 - Telephone contact 6: Week 66
- Visit 10: Week 70
- Visit 11: Week 72/Optional extension period
- Visit 12: Follow-up Visit; Week 76 (for those not participating in optional extension period)
- Optional extension period visits every 16 weeks; Week 88 and onwards

Additional clinic visits may be required for patients who need direct site assistance including, but not limited to, AE monitoring for safety maintenance.

Informed consent must be obtained prior to performing any study procedures. After signing the informed consent form (ICF), patients will be evaluated for study eligibility and considered enrolled in the study. For Cohort 1, patients who completed 24 weeks, or who withdrew after a minimum of 12 weeks of treatment with A4250 due to intolerable symptoms in Study A4250-

005 and meeting all inclusion criteria and no exclusion criteria are eligible for this study. Patients who withdraw from A4250-005 due to a study drug related AE will not be eligible. For Cohort 2, patients meeting all inclusion criteria and no exclusion criteria are eligible for this study.

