7.1.3.1 Screening Period (Days -56 to 0) (For Cohort 2 only)

If the screening period is expected to be prolonged due to COVID-19 related issues, site follow-up with the medical monitor and investigator is required to determine if the screening period can be extended for another 2 weeks. Determination will be assessed on a case-by-case basis. During this allowed two-week extension period, it is anticipated that no additional testing and assessments will be required. If the screening period is extended beyond two weeks, additional assessments, including but not limited to safety labs, will be required.

Day -56 to Day -35/Clinic Visit S-1

Cohort 2 patients will undergo a Screening Visit up to 56 days prior to the planned first day of study treatment. Screening procedures and assessments are as follows:

- Obtain written informed consent
- Assess inclusion/exclusion criteria ([Section 7.2](#))
- Record demographics
- Document concomitant medications
- Medical and surgical history (date of diagnosis of PFIC Type, prior investigational medications for PFIC, historical liver function test [LFT] values, any surgery performed, any other diagnosis, and historical liver biopsy data)

- For patients with episodic forms of PFIC (i.e., BRIC), collect information on frequency, duration, and severity of flares within the last 6 months at a minimum, and within the last 5 years, if possible. If available, historical data on serum bile acid levels and pruritus should be collected
- Collect, if available, past confirmatory clinical genetic laboratory report for PFIC, including BRIC, type and send to central reader for review. If a historical report is equivocal, unavailable, or unobtainable, a blood sample for clinical genetic testing will be collected to determine eligibility ([Section 10.2.4](#))
- Physical examination ([Section 10.2.5](#)) and vital signs ([Section 10.2.6](#))
- Skin examination ([Section 10.2.5](#))
- eDiary training and compliance requirements; caregivers and/or patients begin daily recording of pruritus using the eDiary ([Appendix 2](#))
- Clinical chemistry ([Section 10.2.1](#))
- Serum bile acids ([Section 9.2.1](#))
- Serum pregnancy test for girls who have reached menarche. Please see [Appendix 6](#) for contraceptive requirements
- AE monitoring

Day -28 to Day -7/Clinic Visit S-2

A second Screening Visit will be performed for patients in Cohort 2. Screening procedures and assessments are as follows:

- Review concomitant medications

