7.2.1 Inclusion Criteria

Cohort 1:

1. Completion of the 24-week Treatment Period of Study A4250-005 or withdrawn from Study A4250-005 due to patient/caregiver judgment of intolerable symptoms after completing at least 12 weeks of treatment. Patients who withdraw from A4250-005 due to a study drug related AE will not be eligible.
2. Signed informed consent and assent as appropriate. Patients who turn 18 years of age (or legal age per country) during the study will be required to re-consent to remain on the study.
3. Patients expected to have a consistent caregiver for the duration of the study.
4. Caregivers (and age-appropriate patients) must be willing and able to use an eDiary device as required by the study.

Cohort 2:

1. A male or female patient of any age, with a clinical diagnosis of PFIC, including episodic forms (i.e., BRIC), and with a body weight ≥ 5 kg at Visit S-1.
2. Patient must have clinical genetic confirmation of PFIC.

3. Patients with PFIC, excluding BRIC, must have elevated serum bile acid concentration, specifically measured to be $\geq 100 \mu\text{mol/L}$, taken as the average of 2 samples at least 7 days apart (Visits S-1 and S-2) prior to the Screening/Inclusion Visit (Visit 1).
4. Patients with PFIC, excluding BRIC, must have history of significant pruritus and a caregiver-reported observed scratching or patient-reported itching (for patients >18 with no caregiver-reported observed scratching) in the eDiary average of ≥ 2 (on 0 to 4 scale) in the 2 weeks prior to the Screening/Inclusion Visit (Visit 1).
5. Patients with episodic forms of PFIC (i.e., BRIC) must have an emerging flare characterized by clinically significant pruritus and elevated serum bile acid levels/cholestasis as judged by the investigator.
6. Patient and/or legal guardian must sign informed consent (and assent) as appropriate. Patients who turn 18 years of age (or legal age per country) during the study will be required to re-consent in order to remain in the study.
7. Age appropriate patients are expected to have a consistent caregiver for the duration of the study.
8. Caregivers and age-appropriate patients (≥ 8 years of age, if able) must be willing and able to use an eDiary device as required by the study.

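### For Cohort 2 excluding BRIC, half of the bile acid baseline and all of the diary baseline are the data that decided eligibility, so part of the uncontrolled change may be regression to the mean

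*Protocol*

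**What the plan says.** **Entry (Protocol Section 7.2.1, Cohort 2, criteria 3 and 4).** "Patients with PFIC, excluding BRIC, must have elevated serum bile acid concentration" of at least 100 µmol/L, "taken as the average of 2 samples at least 7 days apart (Visits S-1 and S-2) prior to the Screening/Inclusion Visit (Visit 1"). They also need an average eDiary score of at least 2 ("on 0 to 4 scale) in the 2 weeks prior to the Screening/Inclusion Visit (Visit 1")). BRIC patients enter on an investigator-judged flare with no numeric threshold.

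**Baseline (Section 11.2.2.5).** For fasting bile acids, "baseline will be calculated as the average of Visit S-2 and the pre-dose Visit 1 values in Study A4250-008 for Cohort 2". For pruritus, "Baseline will be defined as the average score from 14 days prior to treatment start in Study A4250-008 for AM and PM, respectively". The bile acid end value is the mean of Weeks 70 and 72.

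**Timing and repeat screening (Section 7.1.1).** Visit 1 is the first treatment day: "Visit 1: Screening/Inclusion Visit (Day 1"). Re-screening is possible after consultation with the Medical Monitor, within this limit: "Patients not fulfilling inclusion/exclusion criteria after 3 attempts are not allowed to rescreen".

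**Other data collected.** From Visit S-1 (Days -56 to -35), "caregivers and/or patients begin daily recording of pruritus using the eDiary" (Section 7.1.3.1), so a diary exists before the eligibility window opens.

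**The concern.** A patient admitted because a measurement exceeded a cut-off will, on average, have had an upward chance deviation in that measurement. If the same measurement is then the baseline, the deviation disappears by the next independent measurement and is recorded as improvement, even with no drug effect. Repeat screening gives further chances of catching a high value.

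Cohort 2's primary objective is to evaluate the effect of A4250 on bile acids and pruritus (Section 6.1), and it has no concurrent control. Change in bile acids is the primary endpoint outside the US and a secondary endpoint in the US; change in scratching and itch severity is exploratory. Section 11.2.2.1 also pools Cohort 2 excluding BRIC with Cohort 1 and with the Cohort 1 placebo-switch group, so the pooled summaries would carry a diluted share of the same artefact. Section 11.2.2.5 fixes these baselines and names no baseline free of the selection.

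**Working it through.** **1. The plan's own figure.** The protocol gives none on this point. Its only power figure (89% to 96%) concerns surgery, transplantation or death. It reproduces with an exact binomial interval (89.8% at n=48, 96.6% at n=60) and has no bearing here.

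**2. Overlap, non-BRIC Cohort 2.**

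| | Decides entry | Forms baseline | Shared |
|---|---|---|---|
| Bile acids | S-1, S-2 | S-2, Visit 1 | S-2: half the baseline |
| Diary | 2 weeks before Visit 1 | 14 days before first dose | all |

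Visit 1 is Day 1, so the two diary windows coincide.

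**3. Bile acids.** Write each sample as the patient's usual level plus an error e. If visits are independent, the Visit 1 and end-value errors average zero among eligible patients, so with no drug effect

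spurious change = -½ × E[e at S-2 | (S-1 + S-2)/2 ≥ 100].

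The protocol gives no variances. Assumed: lognormal values, population mean/SD 250/150, 150/100 or 120/80 µmol/L, within-patient CV 20%, 40% or 60%, and one or three attempts. Simulated examples:

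- 150/100, CV 40%, one attempt: S-2 alone falls by 7.556; half is 3.78; the simulated change from the planned baseline is -3.785. Relative to the baseline of 200.0, that is 1.9%.
- Same inputs, three attempts: -5.332 on 185.2, or 2.9%.
- All scenarios: -0.4 to -13.0 µmol/L (-0.2% to -7.9%). With Visit 1 alone: -0.1 to +0.3 µmol/L.

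A second set of assumptions (median 120 to 250 µmol/L, between-patient log-SD 0.6 to 0.8, within-patient log-SD 0.25 to 0.6) extends the lower end to about 0.3 µmol/L (0.1%). If neighbouring samples correlate at 0.3, the bias reaches about 20 µmol/L (12%) in the worst case, and Visit 1 alone removes roughly half.

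**4. Cost of a single-sample baseline.** With within-patient variance σ² and independent visits, the variance of one patient's change is σ²/2 + σ²/2 = σ² as planned, and σ² + σ²/2 = 1.5σ² from Visit 1 alone. The SE ratio is √1.5 = 1.22. Over 36 scenarios of the second set at n=60, the planned baseline had the lower root-mean-square error in 35 (for example 15.0 against 17.9 µmol/L at median 180, log-SDs 0.6 and 0.4, three attempts). The exception was median 120, log-SDs 0.6 and 0.6, three attempts (21.1 against 20.1). In all 36 the bias was below one SE.

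**5. Mean scratching score.** Assumed: integer scores 0 to 4, population mean 2.0 or 2.5, between-patient SD 0.7, period-to-period SD 0.2 to 0.6, day-to-day SD 0.6, one or three attempts. Spurious change: -0.03 to -0.39 points. A second set (mean 2.2 to 2.8, SD of a 14-day mean 0.2 to 0.5) gives 0.01 to 0.26.

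For scale, take period SD 0.4 and 28 ratings per window. The SD of a window mean is √(0.4² + 0.6²/28) = 0.416, and the SE of the mean change between two windows at n=60 is 0.416 × √2/√60 = 0.076. The simulated bias at that period SD runs from 0.095 (mean 2.5, one attempt) to 0.226 (mean 2.0, three attempts), or about 1.3 to 3.0 SE.

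**6. Proportion of positive assessments.** An assessment is positive if the score is 1 or less, or at least one point below baseline. Scores are integers. With a baseline mean below 3, a one-point drop requires a score below 2, hence 1 or less, which already counts. The baseline value matters only when the AM or PM mean is 3 or more. Simulated positive shares with no drug effect are 10.0% to 30.1% with the planned baseline and 9.9% to 28.4% with an independent one; the largest difference within a scenario is 26.8% - 25.0% = 1.8 points.

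**The case against.** The strongest objection is that the bile acid baseline is a reasonable choice. S-1 is already left out, Visit 1 plays no part in the threshold, and the two-sample mean matches both the Cohort 1 baseline and the two-sample end value. Step 4 shows that changing to Visit 1 alone usually loses more precision than it gains in bias. This stands, and it rules out replacing the primary baseline.

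The size also rests on assumptions. The larger bile acid figures need a population close to the cut-off, whereas Section 5.2.1 describes bile acids in PFIC as very high; at median 250 µmol/L with independent visits the bias is at most 1.8%. Re-screening needs Medical Monitor consultation and may follow failure of any criterion, so three attempts is an upper limit. This stands too.

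The analysis is mainly descriptive, and the one-sample test on bile acids uses Baseline 1, which exists only for Cohort 1. That removes a type I error concern but not a bias in the reported mean. The exploratory comparison with Study 005 placebo covers only the first 24 weeks at 120 µg/kg/day and does not undo the selection.

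A reader might infer that regression to the mean is being presented as the drug effect, that the US primary endpoint is compromised, or that all of Cohort 2 is affected. The documents support none of these. The artefact is at most a part of the change, the positive-assessment rule is nearly insensitive to the baseline, and BRIC patients face no numeric threshold and are presented separately.

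The SAP, which I have not seen, may already contain sensitivity baselines; if so, the point is met.

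**Conclusion.** The point holds for Cohort 2 excluding BRIC. The overlap is explicit in the text, and on average its effect favours the drug. For bile acids it is small: about 0.3 to 13 µmol/L (0.1 to 8%), below one SE at n=60 if visits are independent, and larger if neighbouring samples correlate. For mean scratching score it is 0.01 to 0.39 points, which can exceed the sampling error of the mean change, so this is where it matters most, though only for exploratory endpoints. For the US primary endpoint it is negligible (0 to 1.8 percentage points).

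All sizes depend on assumed variances and population levels. The n=60 used for scale is the whole of Cohort 2 including BRIC; with fewer non-BRIC patients the bias is unchanged and the SEs are larger. This is an inexpensive improvement to the plan and does not call for a different primary analysis.

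**What to change.** Keep the planned baselines as primary. Add to Section 11.2.2.5, for Cohort 2 excluding BRIC, two pre-specified sensitivity analyses reported beside the planned results:

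- (a) bile acid change from the pre-dose Visit 1 value alone, which is what Baseline 2 in Section 11.2.2.1 would give without the special averaging rule;
- (b) change in scratching and itch severity from the screening diary between Visit S-1 and Day -15, about 3 to 6 weeks of entries given that S-1 falls on Days -56 to -35.

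State there that the uncontrolled Cohort 2 change may include regression to the mean.

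The cost is wording and analysis work; no new data are needed. There are three downsides. Baseline (a) raises the SE by about 22%. It removes only part of the bias if neighbouring samples are correlated, and the same limit applies to (b). The earlier diary window may include patients who have just stopped medication that Appendix 1 prohibits from the first day of Screening.

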5.3 Rationale

The investigational product A4250 (non-proprietary name odevixibat; brand name Bylvay) has been approved for the treatment of PFIC by the EMA and for the treatment of pruritus in patients with PFIC by the US FDA. A4250 is also currently being developed for other orphan cholestatic liver diseases.

In PFIC patients with severe pruritus, biliary diversion surgery is used to decrease systemic bile acids through interruption of the enterohepatic circulation and thereby reduce pruritus [Whitington 1988]. Liver transplantation is typically used as an option when patients have failed medical treatment and/or biliary diversion and have liver failure or persistent uncontrolled pruritus.

By inhibiting IBAT with high selectivity and potency, A4250 has the potential to relieve cholestasis and improve liver function without surgical intervention in patients with PFIC. Since A4250 is minimally absorbed and achieves a substantial reduction of serum bile acids, it has the potential to be a safer and less invasive alternative to surgical biliary drainage. The rationale for using A4250 is to decrease serum bile acid levels, and to reduce the major morbidity of pruritus, improving the health and wellbeing of patients affected with PFIC. Ultimately, this noninvasive therapeutic approach has the potential to not only improve QoL, but also reduce the need for biliary diversion and subsequent liver failure and liver transplantation.

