7.2.3 Withdrawal of Patients

Patients/caregivers will be informed that they have the right to withdraw from the study at any time, without prejudice to their medical care, and that they are not obliged to state their reasons.

Any withdrawal, and reasons for withdrawal, must be fully documented in the eCRF and source documents and the patient followed by the investigator/investigative staff. Withdrawn patients will not be replaced.

Patients will be withdrawn in the following circumstances:

- A patient's/caregiver's desire for withdrawal for any reason
- Lost to follow-up (every effort must be made to contact the patient/caregiver; a certified letter must be sent)
- An AE which, in the opinion of the investigator, necessitates withdrawal
- Death
- A patient's/caregiver's substantial non-compliance (eDiary and study drug compliance) or protocol violation
- An investigator's opinion that continuing the patient in the study is not appropriate. The investigator may withdraw a patient at any time, if it is considered to be in the patient's best interest
- Liver transplantation

The reason and the date the patient is withdrawn from the study will be documented in the eCRF and source documents. If a patient is withdrawn from further treatment with the study drug, the investigator/investigative staff will attempt to complete all Visit 11 procedures at the time the patient is prematurely withdrawn from the study. The investigator/investigative staff will also attempt to complete all Visit 12 procedures 28 days following premature withdrawal (i.e., 28 days following the final dose of the study drug).

If a patient discontinues prior to Week 72, additional telephone contacts will be made every 3 months after the Follow-up Visit (Visit 12) up to Week 72 to gather whether or not the patient has had biliary diversion or liver transplantation, and of ongoing TEAEs at the time of discontinuation have resolved. The telephone calls will take place up until 72 weeks even if the patient has biliary diversion or liver transplant.

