9.1.2 Secondary Efficacy Endpoints

EU and rest of world: Proportion of positive pruritus assessments at the patient level over the 72-week treatment period using the Albireo ObsRO instrument.

US: Change from baseline in serum bile acids after 72 weeks of treatment.

All Regions:

- Change from baseline in serum bile acids at Weeks 4, 12, 22, 24, 36, 46, 48, 60, 70, 72, and 76
- Proportion of individual assessments meeting the definition of a positive pruritus assessment at the patient level using the Albireo ObsRO instrument from Weeks 0-4, Weeks 0-12, Weeks 0-22, Weeks 0-24, Weeks 0-36, Weeks 0-46, Weeks 0-48, Weeks 0-60, and Weeks 0-70, respectively, or the proportion of positive pruritus assessments at each 4-week interval between Visit 1/Screening and Visit 5/Week 24, then by each visit between Visit 5/Week 24 to Visit 12/Week 76
- Proportion of individual AM assessments meeting the definition of a positive pruritus assessment at the patient level using the Albireo ObsRO instrument from Weeks 0-4, Weeks 0-12, Weeks 0-22, Weeks 0-24, Weeks 0-36, Weeks 0-46, Weeks 0-48, Weeks 0-60, Weeks 0-70, and Weeks 0-72, respectively, or the proportion of positive pruritus assessments at each 4-week interval between Visit 1/Screening and Visit 5/Week 24, then by each visit between Visit 5/Week 24 to Visit 12/Week 76
- Proportion of individual PM assessments meeting the definition of a positive pruritus assessment at the patient level using the Albireo ObsRO instrument from Weeks 0-4, Weeks 0-12, Weeks 0-22, Weeks 0-24, Weeks 0-36, Weeks 0-46, Weeks 0-48, Weeks 0-60, Weeks 0-70, and Weeks 0-72, respectively, or the proportion of positive pruritus assessments at each 4-week interval between Visit 1/Screening and Visit 5/Week 24, then by each visit between Visit 5/Week 24 to Visit 12/Week 76
- All-cause mortality, number of patients undergoing biliary diversion surgery or liver transplantation. These parameters will be evaluated separately and together at weeks 24, 48, and 72

- Change in growth from baseline to Weeks 24, 48, and 72 after initiation of A4250 treatment, defined as the linear growth deficit (height/length for age, weight for age, mid-arm circumference, and body mass index [BMI]) compared to the standard growth curve (Z-score, standard deviation [SD] from P50)
- Change in AST to platelet ratio index (APRI) score and Fib-4 score from baseline to Week 72

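### Section 11.2.2.5 sets no cut at surgery, so a patient newly diverted on study who stays in follow-up carries post-surgery diary scores and bile acids into the primary endpoints

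*Protocol*

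**What the plan says.** Section 9.1.1 makes change in serum bile acids primary for the EU and rest of world, and the ObsRO pruritus proportion primary for the US. Section 9.1.2 makes each of them secondary in the other region.

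Section 11.2.2.5 defines both:
- Pruritus: "A positive pruritus assessment is defined as a scratching score of ≤ 1 or at least a one-point drop from baseline" on the ObsRO, taken over the 72-week treatment period. "Both AM and PM pruritus assessments will be included in the analysis of this endpoint".
- Bile acids: "The end value is the average of the values at Weeks 70 and 72 in study A4250-008".

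Section 11.2.1 defines the full analysis set as everyone with at least one dose and adds: "The FAS will be the primary analysis set for all analyses unless otherwise specified".

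Section 7.2.3 lists the circumstances in which a patient is withdrawn. "Liver transplantation" is on the list; biliary diversion is not. Section 11.2.2.2 says "Continued collection of efficacy data for patients who discontinue treatment will be made as far as possible". It leaves to the SAP the handling of missing data and the sensitivity analyses for missingness.

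On what diversion does, Section 5.3 states that "biliary diversion surgery is used to decrease systemic bile acids through interruption of the enterohepatic circulation and thereby reduce pruritus". On how it is counted, Section 9.1.2 has the secondary endpoint "All-cause mortality, number of patients undergoing biliary diversion surgery or liver transplantation". Section 11.2.2.6 puts diversion into the composite event proportion that is compared with an untreated reference population.

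**The concern.** Read together, these sections let surgery enter the primary results as though it were drug effect. A patient who does poorly on A4250 and is then diverted is an event under Section 11.2.2.6. If that patient stays in follow-up, the later low scratching scores count as positive assessments and the later low bile acids become the end value.

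There is no control arm in which the same surgery would occur and offset this. The Cohort 1 objective in Section 6.1 is to show a sustained effect of A4250, and improvement produced by late surgery would look exactly like sustained effect. The one-sample test of bile acid change from baseline 1 to end of treatment, also in Section 11.2.2.5, uses end-of-treatment values that surgery can affect in the same way.

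**Working it through.** **1. The plan's own figure.** Section 11.1 gives power of about 89% to 96% for an upper confidence bound below 30% when the true event proportion is 10%, with n = 48 to 60. With an exact (Clopper-Pearson) one-sided 97.5% bound, the bound stays below 30% for at most 7 events in 48 or 10 in 60. The binomial probabilities of this at 10% are 89.8% and 96.6%, so the figure reproduces. It concerns the event endpoint and is not affected by this point. No figure is stated for either primary endpoint.

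**2. Which patients are affected.**
- Transplanted on study: withdrawn under Section 7.2.3.
- Discontinued first, diverted later: Visit 11 procedures at withdrawal, Visit 12 at 28 days after the last dose, then telephone contacts every 3 months (Sections 7.1.1 and 7.2.3). The calls gather no diary scores or blood samples, so these patients supply almost no later primary-endpoint data.
- Diverted before entry (up to 40 in Cohort 2): baseline already reflects the surgery, so they are not affected.
- Newly diverted and still attending visits and completing the diary: all post-surgery data enter. The point concerns this group only.

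**3. Share of diary data after surgery** (schedule in Section 9.2.2). Entries are daily for 24 weeks, then for 21 days before each later visit. The Week 48 and Week 72 windows each overlap the preceding one by 7 days.
- Days to Week 72: 168 + 21 + 21 + 14 + 21 + 21 + 14 = 280, or 560 AM and PM assessments.
- After a Week 12 diversion: (84 + 112)/280 = 70%.
- After Week 24: 112/280 = 40%.
- After Week 48: (21 + 21 + 14)/280 = 20%.

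**4. Bile acids.** The end value uses Weeks 70 and 72 only, so after any diversion before Week 70 it is entirely post-surgical.

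**5. Illustrated size.** The rates and effects are assumptions; the documents give none. Let f be the fraction of patients newly diverted and staying in follow-up. Take f = 10%, borrowed from the Section 11.1 example. That example is for a composite, so this treats every event as a diversion in a patient who stays.
- Bile acids: shift in mean = f × extra surgical change. 0.10 × (-50) = -5 and 0.10 × (-250) = -25 µmol/L.
- Pruritus, diversion at Week 24, 20% positive before and 80% after: patient's proportion = 0.60 × 0.20 + 0.40 × 0.80 = 0.44, against 0.20 if post-surgery assessments are excluded. Shift in mean = 0.10 × 0.24 = 2.4 points.
- Range, excluding post-surgery assessments as comparator: from 0.10 × 0.20 × (0.60 - 0.20) = 0.8 points (Week 48, 60% positive after) to 0.10 × 0.70 × (1.00 - 0.20) = 5.6 points (Week 12, 100% positive after).
- If post-surgery assessments instead count as not positive, the patient's proportion is 0.60 × 0.20 = 0.12 and the difference in the mean is 0.10 × (0.44 - 0.12) = 3.2 points. Part of that gap comes from the scoring rule and not from removing surgical benefit.

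**The case against.** The strongest reply is that no sentence says post-diversion data are kept. Rules for intercurrent surgery often sit in the SAP, and using all observed data is a legitimate treatment-policy choice. The study is mainly descriptive with no formal hypothesis testing. Diversions are reported separately and in the composite, and bile acids are shown by visit and in spaghetti plots, so individual cases could be seen.

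Part of this stands. Retention is inferred from the definitions, the analysis set and the withdrawal list, and a SAP, which was not available here, could add a rule. But the protocol itself fixes both endpoint definitions and, in Section 11.2.2.2, passes only missingness to the SAP. Values after diversion are observed, not missing. Without a control arm, a treatment-policy summary describes drug plus surgery, which is not the effect of A4250 named in the objectives. Plots and event tables do not correct the headline mean.

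A reader might also infer that every diverted patient pushes both endpoints towards benefit, or that efficacy data collected after discontinuation widen the problem. The documents do not support either reading. The first requires that the patient stays in follow-up and that surgery outperforms that patient's own response on drug. The second is largely closed off by the telephone-only follow-up.

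**Conclusion.** The point holds in a limited form. Following the protocol as written credits post-surgery improvement to A4250 for patients newly diverted on study who remain under visit and diary follow-up, and the expected direction favours the drug. The schedule shares (40% of diary days after a Week 24 diversion, the full bile acid end value after any diversion before Week 70) follow from the text. The size does not: neither the number of such patients nor the surgical effect can be taken from the documents, so the shifts in the working are illustrations under stated assumptions. The harm is a biased description of sustained effect, and possibly a biased baseline 1 bile acid test. The event endpoint and its power are sound. The rule should be corrected, but the point does not undermine the study.

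**What to change.** Add one paragraph to Section 11.2.2.5. In the main analysis:
- Scheduled ObsRO assessments after a new on-study biliary diversion count as not positive.
- Bile acid values after such a diversion are not used; the end value is the last on-treatment value before surgery. State this as an exception to the general rule against imputation in Section 11.2.2.2.
- The version using all observed data is shown as a sensitivity analysis.

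Say explicitly that patients diverted before entry are unaffected. Surgery dates are already needed for the time-to-first-event analysis in Section 11.2.2.6. Care, withdrawal rules and follow-up do not change. The cost is the wording, one extra table and a possibly less favourable estimate. Counting assessments as not positive is stricter than excluding them, and the sensitivity analysis lets readers compare the main result with the all-data version.
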